## 12.2 General Considerations

This is a randomized phase II study to assess the efficacy of ADT with Radium-223 dichloride compared to ADT alone in newly diagnosed metastatic prostate cancer subjects with bone metastases.

## 12.3 Interim Analysis

An interim analysis of safety is planned after treatment of 51 safety evaluable subjects. If probably or definitely related (attribution = probably, or definitely) SAE proportion is 40% or greater in ADT+R arm compared to the ADT arm then reassessment of dose in combination will be adjusted by lowering radium-223 dose to 27.5 kBq/Kg/dose for subsequent subjects.

In addition, at 24 months, assessment of the number of events will be completed, blind to the arm of treatment. If time anticipated for the number of events required for analysis significantly exceeds 48 months, the study may enroll additional subjects to reach the required number of events.

## 12.4 Analysis Datasets

### Methods of Statistical Analysis

The definitions of the study populations are listed below.

Population	Definition
Enrolled	This will comprise all subjects who meet the eligibility criteria and are registered onto the study.
Evaluable	This will comprise all subjects who receive at least one dose of trial drug and either undergo at least one post-baseline assessment or die before any evaluation.
Intention-to-treat (ITT)	This will comprise all subjects who meet the eligibility criteria and are registered onto the study irrespective of their compliance to the planned course of treatment. (See Intent-To-Treat principle below).

Population	Definition
Per Protocol Set	This will comprise all subjects who received ADT or ADT+R for 1 cycle and have a radiographic assessment post-baseline.
Safety	All subjects who receive 1 dose of treatment will be included in the safety population.
Treated	This will comprise all subjects who have been exposed to the planned course of treatment to any extent.
ALP normalization	Subjects with abnormal ALP at baseline and at least one other post-baseline ALP measure.

Intention-To-Treat Principle - The principle that asserts that the effect of a treatment policy can be best assessed by evaluating on the basis of the intention to treat a subject (i.e. the planned treatment regimen) rather than the actual treatment given. It has the consequence that subjects allocated to a treatment group should be followed up, assessed and analyzed as members of that group irrespective of their compliance to the planned course of treatment.

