#### **4 SUBJECT REGISTRATION**

All subjects must be registered and randomized through the Hoosier Cancer Research Network (HCRN) electronic data capture (EDC) system OnCore. A subject is considered registered when an "On Study" date is entered into OnCore. Subjects must be registered prior to randomization. Subjects must begin therapy **within 5 business days** of randomization.

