### 12.5 Sample Size/Accrual/Study Duration/Replacement Rules

The sample size is 204 eligible and safety evaluable subjects. Accrual of 204 eligible and safety evaluable subjects is expected to take 24 months. Subjects will be followed for 2 years or until the last enrolled subject has progressed, died, has been followed for 24 months, or study is terminated, whichever occurs first. Subjects who are enrolled but do not receive any treatment will be replaced.

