### 12.6 Analysis of Primary Objective

Subjects will be assessed for radiographic progression as described in section 8. Time from first dose of ADT to radiographic progression or death, whichever occurs first, will be calculated for each subject. For subjects who discontinue study treatment due to reasons other than death or investigator assessed progression, every effort will be made to continue tumor assessments on schedule until radiographic progressive disease or subject death. Subjects who do not have radiographic progression or death will be censored at their last measure for radiographic progression. The primary hypothesis test will be conducted at a one-sided 0.1 significance level using a stratified log-rank test. Kaplan-Meier methods will be used to report rPFS graphically by arm including the median rPFS and 12 and 24 month rPFS proportions in the ITT population. The log-rank test without stratification will be used as a sensitivity analysis.

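### Section 12.4 makes eligibility a condition of the ITT set, so read literally a randomized subject later found ineligible leaves the primary analysis; separately, Sections 8.7 and 12.6 give different time origins for rPFS

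*Combined protocol and SAP*

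**What the plan says.** **Analysis set.** In the Section 12.4 table the Enrolled row reads "This will comprise all subjects who meet the eligibility criteria and are registered onto the study". The ITT row has the same core, "all subjects who meet the eligibility criteria and are registered onto the study irrespective of their compliance to the planned course of treatment", and then points to the ITT principle printed under the table. That principle says that "subjects allocated to a treatment group should be followed up, assessed and analyzed as members of that group irrespective of their compliance". Section 4 states: "Subjects must be registered prior to randomization".

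**Primary test.** Section 12.6 says: "The primary hypothesis test will be conducted at a one-sided 0.1 significance level using a stratified log-rank test". That sentence names no population. The next one places the Kaplan-Meier curve, the median and the "12 and 24 month rPFS proportions in the ITT population".

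**Replacement.** Section 12.5 says "The sample size is 204 eligible and safety evaluable subjects" and "Subjects who are enrolled but do not receive any treatment will be replaced". Section 12.1 randomizes 68 + 136 = 204.

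**Time origin of rPFS.** Section 12.6 and the synopsis start the clock at the first dose of ADT. Section 8.8 gives no origin of its own. It uses the term defined in 8.7 and adds death, and 8.7 counts from randomization. Sections 5.5 and 8.6 treat surgical castration as a start of ADT. Section 3.1 lets early-induction subjects begin ADT up to 28 days before registration, and Section 4.1 says that induction status is not a stratification factor.

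**The concern.** An ITT set protects the comparison because membership is fixed at randomization. Here membership also depends on meeting the eligibility criteria, which can be re-judged after the arm is known. Section 5.1 describes no placebo, so site staff know the arm. If subjects were removed as ineligible more often in one arm, and had a different prognosis from those kept, the stratified log-rank test would no longer compare the groups that randomization formed.

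The time origin is a separate matter. The primary endpoint has two starting points in one document. For an early-induction subject, ADT start precedes randomization, and the interval is event-free by construction. A first dose of ADT also does not describe a subject treated by orchiectomy, and it gives no time zero to a randomized subject who never starts ADT.

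**Working it through.** **1. The plan's own figures reproduce.** Inputs from Section 12.1: medians 12 and 19 months (HR = 12/19 = 0.632), one-sided alpha 0.10, power 90%, 1:2 allocation, 24-month accrual, 48-month study, 10% yearly dropout.

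- Schoenfeld events: (1.2816 + 1.2816)² / [(1/3)(2/3)(ln 0.6316)²] = 140.
- Event probability, with exponential times and dropout rate −ln(0.9)/12 per month: 0.780 control, 0.640 radium. Expected events from 68 + 136 = 140.1; N for 140 events = 203.8, that is 204.
- Power at 140 events: Φ(√(140 × 2/9) × 0.4595 − 1.2816) = 90.0%.

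Defining ITT as all randomized subjects changes none of these.

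**2. Reading the ITT rule against Section 4.** The sequence is eligibility, registration, randomization, treatment.

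| Subject | ITT under 12.4 as worded | ITT as all randomized |
|---|---|---|
| Randomized, eligible, treated | in | in |
| Randomized, eligible, never treated | in | in |
| Randomized, later found ineligible | out | in |
| Registered, never randomized | in, but has no arm | out |

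The third row is the one that matters. The allocation principle does not rescue it: it says that compliance is disregarded, not eligibility.

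**3. Possible size; all exclusion rates are assumed.** If 4, 10 or 20 of 204 randomized subjects (2, 5, 10%) were excluded and not made up, expected events would be 137.4, 133.2 and 126.4. The same power formula, with unrounded events, gives 89.6, 88.9 and 87.6%.

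For bias, take a null simulation: 68 v 136, median 12 months, Section 12.1 accrual and dropout, unstratified one-sided log-rank at 0.10. The same fraction of each arm carries 1.5 or 2 times the hazard and is then excluded from one arm only (10,000 trials) or from both (6,000).

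| Excluded fraction | Radium arm only: change in type I error | Control arm only: change |
|---|---|---|
| 2% | +0.8 to +1.1 points | −0.5 to −0.9 |
| 5% | +2.0 to +3.3 | −1.5 to −2.3 |
| 10% | +4.6 to +8.1 | −3.3 to −4.9 |

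Excluded from both arms, type I error is 10.4 to 10.8%. With no difference in hazard, it changes by 0.25 point or less.

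**4. Replacement.** Sections 12.1 (204 randomized) and 12.5 (204 eligible and safety evaluable) agree only if every randomized subject is eligible and treated. If 204 means treated subjects and 2, 5 or 10% of those randomized are never treated (assumed), then 204/0.98, 204/0.95 and 204/0.90 give 208, 215 and 227 randomized. The extra 4, 11 or 23, if eligible, are in ITT by 12.4.

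**5. Time origin.** The two origins differ by up to 28 days (about 0.92 month) plus any gap from registration to randomization, against a 7-month target difference. Shifting event times uniformly over 0 to 28 days in 50% or 100% of subjects (6,000 runs) moved power by less than 0.1 point and the null rejection rate by about 0.1 point at most.

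A second null simulation puts scans at days 196, 336 and 699 from ADT start, with leads of 0 to 28 days in early-induction subjects. With induction status falling at random (6,000 trials), type I error on the randomization clock is 10.1% (50% early), 9.6% (50% early, 20% of events deaths) and 10.3% (25% early).

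**The case against.** The strongest reply is that this is loose drafting. The ITT row points to a principle framed in terms of allocation. Eligibility is checked before registration, and no section sets up an eligibility review or a removal step after randomization. That lowers the likelihood of exclusions, but the written rule still permits them, and the principle does not override it.

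A reader might go further in five ways that the documents do not support:

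- **The primary test has no population.** The next sentence of 12.6 names ITT, 12.7 uses ITT for the secondary time-to-event analyses, and no efficacy test is assigned to another set. ITT is evidently meant.
- **Replaced subjects are dropped.** Section 12.5 is an accrual rule, and 12.4 keeps an eligible, registered, untreated subject in ITT.
- **Unrandomized subjects contaminate the test.** They have no arm and cannot enter a two-arm log-rank test.
- **Power falls to 87.6%.** That assumes a fixed 204 with losses not made up. Section 12.5 counts eligible subjects toward its 204, and 12.1 and 12.3 allow added enrolment if the required events would come significantly later than 48 months.
- **Type I error is seriously inflated.** The larger exclusion figures need every exclusion in one arm, and all in subjects at raised hazard; they also come from an unstratified test. For the origin, values of 14.0 to 15.5% and 20.3 to 23.6% arise on the randomization clock only given a chance early-induction excess in the control arm of 10 or 20 points. At 50% early induction, gaps that large in either direction have probability of about 18% and 0.7%, and the inflating direction is half of that. Averaged over chance, the rate is about 10%.

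**Conclusion.** The point holds as a defect in the definition of the primary analysis set: eligibility should not be a condition of ITT membership after randomization. Its effect cannot be sized from the documents, which give no rates of late ineligibility. It is nil to small if exclusions are few, balanced or unrelated to prognosis. It becomes material only if they are both arm-related and prognostic: under the assumed one-arm cases, 2% exclusion moves type I error by about one point and 10% by up to 8.1 points. The 140 events and 204 subjects are unaffected.

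The time origin is a plain conflict between 8.7, carried into 8.8, and 12.6 with the synopsis. It matters for a single readable definition and for the reported medians and 12- and 24-month proportions. It does not matter for overall type I error.

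Both are worth correcting before the data are seen. Neither shows that the planned test is invalid.

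**What to change.** **12.4:** define ITT as all randomized subjects, analysed in the arm assigned, whatever is later found about eligibility or treatment received. Report registered but unrandomized subjects in the subject flow only.

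**12.6 and synopsis:** name ITT in the stratified log-rank sentence.

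**12.5:** say that replacement affects accrual only, and that a replaced subject who was randomized stays in ITT.

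**8.7, 8.8, 12.6 and synopsis:** state one rPFS origin. Either is defensible. Randomization gives every randomized subject a time zero. ADT start matches the scan schedule; if it is kept, use the wording of 8.6 so that surgical castration is covered. Say how a randomized subject who never starts ADT is timed (for example, from randomization), and report the other origin as a sensitivity analysis.

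**Cost:** a wording amendment, with no change to the event or subject targets. The practical downside is that a few randomized subjects who prove ineligible or are never treated must stay in scan follow-up.

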### 12.5 Sample Size/Accrual/Study Duration/Replacement Rules

The sample size is 204 eligible and safety evaluable subjects. Accrual of 204 eligible and safety evaluable subjects is expected to take 24 months. Subjects will be followed for 2 years or until the last enrolled subject has progressed, died, has been followed for 24 months, or study is terminated, whichever occurs first. Subjects who are enrolled but do not receive any treatment will be replaced.

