### 7.10 End of Treatment (EOT) and Follow Up

The end of treatment/follow up column will be utilized for subjects that come off protocol therapy (radium-223 dichloride if randomized to that Arm and ADT) for toxicity or progression. If this occurs, subjects should have an end of treatment visit 30 days ( $\pm$  7 days) after discontinuation of protocol therapy. Subjects will then continue to be followed every 3 months for a total of 2 years from the date of randomization. Follow up may occur via phone call, email or other communication. If available by medical record review, alk phos, PSA, AE/concomitant medication should be obtained. Testing to be done at the EOT visit:

- Circulating tumor cell's (CTCs)
- Serum bone turnover markers
- Banking Samples: serum, plasma
- Alkaline phosphatase
- PSA

If a subject withdraws consent, he is deemed **“off study”**. “Off study” subjects will not be followed further.

A subject will be discontinued from the protocol specified therapy under the following circumstances:

- If there is evidence of radiologic disease progression or symptomatic deterioration despite castration range serum testosterone level ( $< 50$  ng/dL). Such subjects can go on to other treatment outside the study as clinically indicated including continuation or initiation of radium-223 dichloride therapy. They will remain on follow-up portion of the study for a total of 2 years from the date of randomization.
- If there is development of castration-resistant prostate cancer by PSA criteria in conjunction with castration range serum testosterone level ( $< 50$  ng/dL). Castration resistant prostate cancer is defined as two consecutive increases in PSA over the nadir PSA, at least two weeks apart **AND** an absolute increase of at least 2 ng/mL from the nadir PSA (or from baseline PSA if there was no drop in PSA after starting treatment). Discontinuation of bicalutamide may be attempted at the investigator's discretion in such cases and would NOT constitute going “off treatment”. If no response to bicalutamide discontinuation, such subjects may receive other treatment outside the study as clinically indicated including continuation or initiation of radium-223 dichloride therapy. They will remain on follow-up portion of the study for a total of 2 years from the date of randomization.

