## **12. STATISTICAL CONSIDERATIONS**

### **12.1 Study Design**

Newly diagnosed metastatic prostate cancer subjects with  $\geq 2$  bone metastases will be accrued and randomized 1:2 to ADT without or with Radium-223 dichloride respectively. The primary aim of the study is to determine if the addition of Radium-223 dichloride to ADT will improve efficacy in this prostate cancer population. The primary efficacy endpoint is radiographic progression-free survival (rPFS). We expect the control arm with ADT alone to have a 12 month median rPFS. The addition of radium-223 to ADT will target an improvement of 7 months for a median rPFS of 19 months. A total of 140 events are required for at least 90% power to detect Hazard Ratio of 0.632 with a one-sided alpha of 0.1. The study powering is based on assumptions of 19 months median rPFS in the experimental arm and 12 months median rPFS in the control arm. Assuming exponential time to event data, a yearly dropout rate of 10% with

accrual in 24 months and study duration of 48 months, 204 subjects will provide 90% power with a 10% one-sided type I error. Hypothesis testing for the primary endpoint will be conducted at a one-sided 0.10 significance level using a stratified log-rank test. Randomization of 68 subjects to the ADT arm and 136 subjects to the ADT+R arm will be completed with stratification by extent of disease (<6 skeletal metastases without visceral disease versus  $\geq 6$  skeletal metastases or visceral disease) and baseline alkaline phosphatase (normal versus abnormal), abnormal alkaline phosphatase defined as  $> 130$  IU/L. If time anticipated for the number of events required for analysis significantly exceeds 48 months, the sponsor may enroll additional subjects to reach required number of events.

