### 12.7 Analysis of Secondary Objectives

Toxicity will be described within each arm by type, maximum grade and frequency among the safety population. The proportion of subjects in each arm with skeletal related events and secondary neoplasms will be reported individually and a mid p-value test will compare the proportions between arms.

Time to castration resistance (TTCR), PSA progression free survival (PCWG2 criteria), and Overall Survival (OS) will be reported by arm using Kaplan-Meier methods and tested using the log-rank test. The –time to castration resistance, the 2-year PSA PFS and OS proportions with 90% confidence intervals will be reported using Kaplan-Meier methods. Analyses will be completed on the ITT population.

Binomial proportions with 90% binomial confidence intervals of subjects who achieve PSA  $\leq$  0.2 ng/mL at 7 months after treatment initiation will be reported by arm. Similarly, the proportions and associated confidence intervals of subjects who achieve PSA  $\leq$  4 ng/mL at 7 months after treatment initiation will be described.

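### Section 12.5 as written lets the last enrolled subject's progression or death end follow-up for all subjects, which contradicts section 7.10, the synopsis and the 48-month power assumption

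*Combined protocol and SAP*

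**What the plan says.** Section 12.5 sets the duration of follow-up. It gives all subjects 2 years, with this alternative end: "until the last enrolled subject has progressed, died, has been followed for 24 months, or study is terminated, whichever occurs first". The people being followed are all subjects, but three of the four listed triggers concern one man only. The section does not say which kind of progression counts, although section 8.2 defines PSA, bone-scan and soft-tissue progression separately.

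Other places say something different:

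- Section 7.10, on subjects taken off therapy for progression: "They will remain on follow-up portion of the study for a total of 2 years from the date of randomization". Calendar footnote 14 sets the same 2 years from randomization.
- The synopsis gives a total duration of 4 years, split into 2 years of accrual and 2 years of follow-up.
- Section 12.1 bases its 90% power on 24 months of accrual and a 48-month study.
- Section 12.3 counts events at month 24 and allows extra enrolment if the required number would come well after month 48.

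The analyses that depend on two years of data are the 24-month part of the "12 and 24 month rPFS proportions in the ITT population" (section 12.6) and, in section 12.7, "the 2-year PSA PFS and OS proportions with 90% confidence intervals will be reported using Kaplan-Meier methods".

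**The concern.** Taken at its word, section 12.5 makes the closing date of the trial depend on the outcome of whoever happens to enrol last. If that man progressed 7 months after entry, follow-up would stop for every subject enrolled in the 17 months before him, whatever their own status. A reader cannot tell from the protocol whether 12.5 or 7.10 governs.

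At stake are rPFS events for the primary test, the precision of the 24-month rPFS and 2-year PSA-PFS and OS estimates, and late safety information such as secondary neoplasms. The clause also works against the remedy in sections 12.1 and 12.3. If extra subjects are enrolled to reach the event target, the last enrolled subject becomes a later man, and his early progression could close the trial.

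**Working it through.** **Inputs.** Section 12.5: "Accrual of 204 eligible and safety evaluable subjects is expected to take 24 months". Section 12.1: "19 months median rPFS in the experimental arm and 12 months median rPFS in the control arm"; 68 and 136 subjects; exponential times; 10% yearly dropout; 48-month study. Assumptions of this check: uniform accrual, last entry at exactly month 24, and (except where stated) progression or death of the last subject taken as his rPFS event.

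**1. The plan's own figure.** Section 12.1 states: "A total of 140 events are required for at least 90% power to detect Hazard Ratio of 0.632 with a one-sided alpha of 0.1". Schoenfeld's formula gives (1.2816 + 1.2816)² / [(1/3)(2/3)(ln 0.632)²] = 6.570 / 0.0468 = 140.4. At 140 events the power is 89.9%. With everyone followed to month 48 and dropout hazard −ln(0.9)/12 per month, 204 subjects yield 140.1 expected events. The plan reproduces, but only with follow-up to month 48.

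**2. The literal rule, progression detected continuously.** Let T be the last subject's time to rPFS event. Follow-up closes at month 24 + min(T, 24). A subject who entered at month u has 24 months available only if u ≤ min(T, 24), so the expected share falling short is 1 − E[min(T, 24)]/24, where E[min(T, 24)] = (1 − e^(−24λ))/λ and λ = ln 2/median.

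| Last subject's arm | E[min(T,24)], months | Share short | P(T < 24) |
|---|---|---|---|
| Control (median 12) | 12.98 | 45.9% | 75.0% |
| Radium (median 19) | 15.99 | 33.4% | 58.3% |
| 1:2 mixture | 14.99 | 37.5% (about 77 of 204) | 63.9% |

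The spread is wide: no loss with probability 36%, median loss 32%, upper quartile 72%, 90th percentile 90%. If the last subject can himself drop out before an event, the rule fires with probability 59%, the mean loss is 35% and the median 25%.

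**3. The same rule, progression recognised only at scheduled scans.** Calendar footnote 8 places post-baseline scans at C8D1, C13D1 and C17D28. With 28- and 84-day cycles these fall at days 196, 336 and 700, or about 6.4, 11.0 and 23.0 months. The simplifications are that deaths are assigned to the next scan and that times from C1D1 are treated as times from entry. Under the 1:2 mixture:

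| Rule fires at | Probability | Share short |
|---|---|---|
| 6.4 months | 24.3% | 73.2% |
| 11.0 months | 13.5% | 54.0% |
| 23.0 months | 24.5% | 4.2% |
| Not before 24 months | 37.6% | 0% |

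Mean: 0.243 × 73.2% + 0.135 × 54.0% + 0.245 × 4.2% = 26%. It is about 24% if the last subject can drop out. The median is about 4%. The chance that at least 10% of subjects fall short is about 35–38%, against about 60% (ignoring dropout) with continuous detection.

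**4. Who is actually cut off.** The 37.5% counts potential follow-up. Many of those men would already have had an rPFS event. Those cut off before 24 months while still rPFS-event-free are about 20% of all subjects, or 18% allowing for dropout (continuous detection). For OS, under assumed medians of 28 to 58 months, about 26% to 31% would be cut off alive.

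**5. Events and power** (continuous detection, dropout included).

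| Follow-up rule | Expected rPFS events | Power |
|---|---|---|
| All to month 48 | 140 | 90% |
| 24 months per subject | 120 | 86% |
| 24 months per subject plus last-subject clause | 108 | 83% |

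For the middle row, the probability of an observed event by 24 months is 0.692 (control) and 0.534 (radium): 68 × 0.692 + 136 × 0.534 = 119.7.

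**The case against.** The best defence is that nobody would run the trial this way. Section 7.10, footnote 14, the synopsis and section 12.1 all point to two years for each subject and a 48-month study, and the event check in 12.3 makes little sense if one man's progression could close follow-up. The clause may be a clumsy end-of-study definition. That stands to this extent: the matter is an internal inconsistency, and every loss figure above is conditional on 12.5 being followed literally. It does not remove the problem, because no section says which rule prevails and 12.5 is the section that sets duration.

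Several stronger readings are tempting and are not supported:

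- A reader might infer that about 38% of subjects will fail to reach 24 months. That needs 12.5 to override the other sections and progression to be seen continuously.
- A reader might infer that most realizations would lose a large block of subjects. Under the scan schedule, about 62–65% of realizations lose less than 10%.
- A reader might infer that every time-point estimate needs 24 months per man. The 12-month rPFS proportion does not, and Kaplan-Meier accommodates this administrative censoring, so bias is not the issue.
- A reader might attribute the whole drop from 140 to 108 events to this clause. The step from 140 to 120 comes from the per-subject 2-year limit, which is a separate matter.

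One might also argue that PSA progression would trigger the clause earlier. With an assumed 8-month median the mean loss would be about 58%, but 12.5 does not give the word that meaning.

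**Conclusion.** The concern holds as a contradiction that should be reconciled. As written, section 12.5 lets one subject's progression or death end follow-up for all, against section 7.10, footnote 14, the synopsis and the 48-month basis of the power.

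If followed literally, the mean share without 24 months of potential follow-up is about 38% with continuous detection, or about 24–26% (median about 4%) with recognition at scheduled scans. The clause's own cost under continuous detection is about 12 expected rPFS events (120 to 108) and about 3 points of power (86% to 83%). The corresponding event loss under scan-based recognition was not calculated.

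These figures rest on the plan's medians, allocation and exponential model, and on assumed uniform accrual with the last entry at month 24. The harm is lost events and precision at 24 months.

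**What to change.** In section 12.5:

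1. Delete the last enrolled subject's progression and death as conditions that end follow-up for the study.
2. State that each subject is followed for 2 years from his own randomization, as in section 7.10, or until his own death or withdrawal of consent, and that progression of any subject does not end follow-up. Keep the fixed 2-year total: calling it a minimum would create a new conflict with 7.10 and footnote 14.
3. Set the data cut-off no earlier than 24 months after the last subject is randomized, unless the study is terminated, consistent with the 48 months in the synopsis and section 12.1 and the event check in section 12.3.

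Under the assumptions above, this takes the share cut short by the clause to zero and restores expected rPFS events from about 108 to about 120. It does not by itself reach 140, which needs follow-up to month 48 and should be settled separately.

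The cost is a short wording change with no added subjects. The downside is that the trial may run the full 48 months already planned.
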